3.5.3 Propensity Score Set

A subset of the Enrolled Set, the Propensity Score Set will be created using the rules in Section 8.1.2 in order to create a population with treatment cohorts with similar Baseline variables.

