6.4 Statistical Analyses

All analyses will be performed on the eligible population, defined as all patients enrolled in this non-interventional study that meet eligibility requirements. All data captured from enrollment to last completed follow-up (Investigator or direct-to-patient) will be included.

Specifics to the primary and secondary analyses are outlined below and described in more detail in the SAP. All statistical analyses will be conducted using SAS version 9.1.3 or higher.

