3.4 Protocol deviations

An important deviation is defined as a deviation from the protocol which could potentially have a meaningful impact on the primary outcome of this study, and are defined as follows:

1. Patient did not sign informed consent.
2. Patient did not have medically documented CD.
3. Patient under 18 years (from protocol amendment 3 onwards)
4. Patient participates in a randomized & blinded clinical trial.
5. Cimzia Cohort patient does not receive Cimzia within 2 months after enrollment (Window of 7 days is allowed).
6. Comparison Cohort patient receives Cimzia prior to enrollment.
7. Comparison Cohort patient does not receive comparator treatment within 2 months after enrollment (Window of 7 days is allowed).
8. Patient is enrolled at more than one site.
9. Any other deviation that the study team determines to be an important deviation over the course of the study.

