3.5 Analysis sets

3.5.1 Enrolled Set

All Analyses will be performed on the Enrolled Set, defined as all patients enrolled and with an informed consent. Subjects that were enrolled at more than one site were excluded from the Enrolled Set (See Analysis Data Reviewers Guide for details).

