3.5.2 Full Analysis Set

All analyses will be conducted on the Full Analysis Set, defined as all patients enrolled in this non-interventional study that meet eligibility requirements. All data captured from enrollment to last completed follow-up (physician or direct-to-patient) will be included.

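### The Propensity Score Set is drawn from the Enrolled Set with no eligibility filter, so patients outside the protocol's eligible population, including comparators with prior Cimzia, can be scored and matched

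*SAP*

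**What the plan says.** Protocol 6.4 sets one analysis population: "All analyses will be performed on the eligible population", meaning enrolled patients who satisfy the entry criteria. SAP 3.5.2 repeats this: "All analyses will be conducted on the Full Analysis Set, defined as all patients enrolled in this non-interventional study that meet eligibility requirements".

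SAP 3.5.1 makes the same claim for a wider set: "All Analyses will be performed on the Enrolled Set, defined as all patients enrolled and with an informed consent". Its only further exclusion is "Subjects that were enrolled at more than one site were excluded from the Enrolled Set".

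SAP 3.5.3 then names the wider set as the source for matching, with Section 8.1.2 as the rule for building it: "A subset of the Enrolled Set, the Propensity Score Set will be created".

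The rationale for SAP Amendment 5 (Section 12.5) says that analyses rest on the Full Analysis Set (FAS) and, in addition, on the Enrolled Set (ES). SAP 3.5.3 does not mention the FAS.

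Protocol 4.3 and SAP 2.3.1 bar earlier Cimzia use in comparator patients. SAP 3.4 still foresees it, listing "Comparison Cohort patient receives Cimzia prior to enrollment" among the important deviations, which it defines as those that could meaningfully affect the primary outcome. No exclusion is attached to it.

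**The concern.** Protocol 6.4.1 says that propensity scores are to be part of the primary analysis, and malignancy is the primary outcome. The matched comparison is the one meant to control confounding, so the patients admitted to it should be those on whom the protocol says analyses are done. As written, the SAP admits a wider group, and its two general statements about analysis sets contradict each other.

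Two things are at stake. First, a matched result on the ES need not describe the same patients as the FAS rates, so a difference between them could reflect population as well as confounding control. Second, a comparator with prior Cimzia is sorted by cohort label for matching but by exposure history for malignancy. The two rules place the same patient on opposite sides.

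**Working it through.** No formula in the plan applies here, so the check is a comparison of texts.

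**1. Which foreseen deviations the Enrolled Set removes.** The list is in SAP 3.4 and the set definition in SAP 3.5.1.

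| Important deviation (SAP 3.4) | Removed by the ES definition? |
|---|---|
| 1. No informed consent | Yes |
| 2. No documented Crohn's disease | No |
| 3. Under 18 (from protocol amendment 3) | No |
| 4. In a randomized, blinded trial | No |
| 5. Cimzia Cohort, no Cimzia within 2 months after enrollment | No |
| 6. Comparison Cohort, Cimzia before enrollment | No |
| 7. Comparison Cohort, no comparator treatment within 2 months after enrollment | No |
| 8. Enrolled at more than one site | Yes |

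Item 9 is an open category. Items 2 to 7 correspond to entry criteria in SAP 2.3.1. The FAS would remove such patients and the ES does not.

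**2. Whether Section 8.1.2 filters later.** SAP 3.5.3 names this section as the rule for building the set.

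- 8.1.2.1 models treatment cohort by logistic regression.
- 8.1.2.2 discards patients outside common support, and chooses the caliper to keep the sample from all enrolled patients as large as possible.
- 8.1.2.3 computes a score for every patient in the database and drops those with no match within the caliper.

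None of these steps tests eligibility. The covariate list names other biologics, immunosuppressants and corticosteroids in the prior year. It does not name prior Cimzia, although the list is open-ended.

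**3. Following one patient: Comparison Cohort, Cimzia before enrollment.**

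- Label: SAP 3.6 keeps the recorded enrollment cohort whatever the medication history shows, so the patient remains a comparator.
- Matching: the patient can be the control in a 1:1 pair.
- Malignancy attribution: SAP 3.2.1.1 assigns to Cimzia any malignancy after Cimzia exposure, including known use before enrollment. In Appendix 1, scenario 1b gives all time from consent to end of study to Cimzia and none to comparator. Scenarios 3b and 17b do the same up to the malignancy date, although the on-study treatment begins with comparator or with a gap followed by comparator.
- Result: the pair contains no comparator time for the primary outcome.

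In symbols, take n matched pairs of which m have such a control. Suppose every Cimzia Cohort member has been exposed and no other control receives Cimzia. The malignancy rule then compares n + m patients with n − m, not n with n, and m pairs contain no contrast.

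Under the acute-event rules the same patient's time on comparator stays comparator, because Appendix 1 says that dosing before consent affects malignancy time only. A dose within 70 days before baseline would also place the patient in the Cimzia at BL group that SAP 3.6 uses for the hazard ratio.

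**4. Whether the size can be computed.** SAP 2.4 gives 3076 enrolled at final analysis, and 1371 + 1674 = 3045 as of March 2017. No count of ineligible patients, or of comparators with prior Cimzia, appears anywhere. The value of m is unknown and may be 0.

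**5. Whether eligibility could be applied after matching.** Removing one member of a 1:1 pair leaves the other unmatched, and the balance checked under 8.1.2.4 would no longer describe the patients analysed. Eligibility therefore has to come before score estimation.

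**The case against.** The strongest reply is that SAP 3.5.2 already puts all analyses on the FAS and Amendment 5 confirms it, so 3.5.3 is leftover wording. That is plausible as intent. But 3.5.1 makes the same claim for the ES, and 3.5.3, the only specific statement, names the ES. A programmer following the text would start from the ES.

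A second reply is that eligibility includes treatment within 2 months after enrollment, so restricting to the FAS selects on something that happens after entry. This is a real trade-off, but the protocol has already made that choice for all analyses.

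A third is that erroneous entries are handled in the Analysis Data Reviewers Guide, which is not among the documents. It might remove some of these patients. This limits the point to what the protocol and SAP say.

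Some stronger readings are tempting but not supported:

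- A reader might infer that a fixed share of each arm is mislabelled and that the matched ratio is pulled toward 1 by a calculable amount. The documents give no such share. The rate and time-to-event rules (SAP 3.6, 8.1.3, 8.1.4) attribute by actual exposure, and the exposure variable in the matched outcome model is not stated. For malignancy the consequence is a pair without a contrast, which a symmetric mislabelling formula does not describe.
- A reader might infer that every ineligible patient is in the wrong arm. A patient without documented Crohn's disease is a population error, not an exposure error. Deviation 5 means no dose within 2 months after enrollment. It does not mean never dosed, since such a patient may have been on Cimzia before enrollment or may start later.
- A reader might infer that the matched set shares no population with the main rates. Amendment 5 has analyses run on the ES as well.

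**Conclusion.** The point holds as a contradiction within the SAP and between the SAP and the protocol. As written, patients outside the eligible population can be scored and matched. A comparator with prior Cimzia can serve as a control while contributing only Cimzia time to the primary outcome.

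The documents show that this can happen, not that it did. Its size cannot be derived. The conclusion rests on reading 3.5.3 and 8.1.2 literally and on no filter being applied in the guide that is not available here. The plan calls its analyses descriptive, so this is a minor correction, worth making because it is cheap and follows the plan's own stated intent.

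Correcting the source set does not remove switching during the study. An eligible comparator who later starts Cimzia will still pass to the Cimzia side from that date, as the plan intends.

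**What to change.** - In SAP 3.5.3, define the Propensity Score Set as a subset of the Full Analysis Set, and state that eligibility is applied before score estimation and matching.
- Keep a version built from the Enrolled Set as a supportive analysis, in line with the Amendment 5 rationale.
- Change SAP 3.5.1 so that it no longer claims all analyses for the Enrolled Set. Editing 3.5.3 alone would leave 3.5.1 and 3.5.2 in conflict.
- Report the number of patients excluded, by reason and enrollment cohort, with comparators who had prior Cimzia shown separately.

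The cost is a few lines of SAP text, a rerun of scoring and matching on the smaller source set, and a somewhat smaller matched set. How much smaller cannot be known from the documents.

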3.6 Treatment assignment and treatment groups

Given that patients will be followed for 8 years, it is anticipated that patients will switch CD medications while enrolled in the registry. Therefore, a patient's treatment at registry enrollment will most likely not reflect their exposure throughout the study. Three comparisons may be used to reflect these treatment changes over time and provide context for events reported to the registry. See Section 8.1.4 for details.

Treatment start is the recording period (ie, the informed consent date). Only study emergent adverse events will be reported. Study emergent begins at the informed consent through the end of the study.

Treatment by enrollment cohort will consist of two groups:

- Cimzia
- Comparator
 - where comparator includes:
 - Corticosteroids
 - Immunosuppressants
 - Other biologics (e.g. anti-TNFs) other than Cimzia

Enrollment cohort is recorded and will be assumed regardless of the presence of prior or imputed CD medication referring to the other treatment group. These are the default treatment groups.

Some summaries will be repeated by actual treatment at Baseline to examine differences between treatment by enrollment cohort. Actual treatment at Baseline will be summarized in three groups:

- Cimzia at BL
- No Cimzia at BL
- Gap (absence of Cimzia and comparator)

Actual treatment will be used for adverse event tables unless specified otherwise. If a patient received Cimzia up to 70 days prior to baseline (half-life of CZP), the patient is a member of the treatment group "Cimzia at BL". For the calculation of the Hazard Ratio, the group 'Cimzia at BL' is compared against the combined group "No Cimzia at BL" and "Gap".

For malignancies, person-time and events will be categorized into 2 groups:

- Cimzia
- Comparator

where a patient is systematically attributed to Cimzia from their first dose of Cimzia until the end of the study, even after ending or switching from Cimzia.

For acute events, person-time and events will be categorized into 5 groups:

- Cimzia
- Comparator
- Overlap (Cimzia and comparator)
- Gap (absence of Cimzia and comparator)
- Any Cimzia (Cimzia and Overlap)

Example treatment allocations for malignancies and acute events are in Section 11.1, appendix 1.

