3.2.1.2 Person-time at risk calculations for acute events

Exposure person-time at risk will be calculated for each CD treatment using the following equation:

$$\text{Last Date} - \text{First Date} + 1$$

First date is defined as the latest enrollment date or first CD treatment date after enrollment (whichever is later) or the first dose of new treatment if switching treatments. Last date is defined as the earliest of the following:

- Date of safety event of interest (for incidence rate calculations only)
- Last dose date + treatment class-specific half-life exposure for product
- Date of discontinuation, withdrawal, or data cutoff

Any gaps in exposure, as illustrated in the figure below, will be included in the gap treatment group person-time at risk calculations for acute events. Any overlap in treatment groups will be included in the overlap group person-time at risk calculations for acute events.

Figure 2: Example person-time at risk for acute events

[figure not shown]

Figure 2 presents an example of a patient's exposure history. For this example, exposure person-time at risk would be calculated as follows:

Exposure person-time = (Last treatment date + Treatment class-specific half-life) – First treatment date + 1) + (earliest of End treatment date + treatment class-specific half-life exposure, last date in study, data cutoff date) – Resume treatment date + 1).

See Section 11.1, appendix 1 for more examples of treatment allocation scenarios for acute events.

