8.1.3 Time-to-event analysis

Time-to-event analyses will be conducted for each Adverse Event of Interest.

Please refer to Section 3.6 for the assignment of treatment groups and to Section 3.2.1 for details on exposure times.

Cimzia vs. Comparator (acute event rules)

Per patient and Adverse Event of Interest, exposure time until the first occurrence of the AE is considered. Prior to the AE, at any given time after treatment start, the patient can be exposed to either of: Cimzia, Comparator, Overlap, or Gap (one at a time but with switches between them). Thus, up to the first occurrence of the AE, 4 exposure times are recorded, one for each treatment. The first occurrence of the AE is counted as event for the actual treatment where it occurred (i.e. exactly one of Cimzia, Comparator, Overlap, or Gap), and exposure time is censored for the remaining 3 treatments. If no AE of interest occurred, time will be censored at the end of exposure for all treatments. The comparison of interest is Cimzia vs. Comparator.

Any Cimzia vs. Comparator (acute event rules)

Per patient and Adverse Event of Interest, exposure time until the first occurrence of the AE is considered. Prior to the AE, at any given time after treatment start, the patient can be exposed to either of: Any Cimzia (i.e. Cimzia monotherapy or Overlap), Comparator, or Gap (one at a time but with switches between them). Thus, up to the first occurrence of the AE, 3 exposure times are recorded, one for each treatment. The first occurrence of the AE is counted as event for the actual treatment where it occurred (i.e. exactly one of any Cimzia, Comparator, or Gap), and exposure time is censored for the remaining 2 treatments. If no AE of interest occurred, time will be censored at the end of exposure for all treatments. The comparison of interest is Any Cimzia vs. Comparator.

Cimzia vs. Comparator (malignancy rules)

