8.1.4 Incidence and event rate calculation

In general, for each, the cumulative incidence, incidence rate and corresponding 95% confidence interval will be presented. For the incidence rate, the numerator will be the total number of patients experiencing the AE of interest for the first time in the study (if a patient switches treatment and has an AE of interest it will be considered a recurrence if the AE occurred while on a previous treatment). The denominator will be in 100 patient-years. That is, the denominator will be the total summation of individual patient-years at risk up the first occurrence of the AE of interest for subjects with that AE, and the total patient-years at risk for those subjects not experiencing that AE, divided by 100. Two-sided 95% confidence intervals for the incidence rates are calculated [using the GAMINV function in SAS] to determine the upper and lower limits for the number of events for each AE of interest, which is assumed to follow a Poisson distribution, divided by the total patient-years of exposure multiplied by 100. [Note that the method to be used follows a SAS implementation using the GAMINV function and is described in detail on bottom, right hand side of p. 2 and the code in the box on the left hand side of p. 3 in the SUGI paper <http://www2.sas.com/proceedings/sugi26/p241-26.pdf>].

A Poisson AE of interest regression analysis, accounting for within-patient correlations, implemented with the GENMOD procedure in SAS, is used to test for the differences in incidence rates between actual treatment cohorts at the two-sided $\alpha=0.05$ level. Potential code for these models is:

```
PROC GENMOD data = XXXXX;  
CLASS COHORT;  
MODEL AEOFINT = COHORT / D = POISSON OFFSET = LPRSNYRS;  
RUN;
```

Where AEOFINT is the number of events for a particular AE of interest, LPRSNYRS is the log of the total number of patient-years, and COHORT represents the actual treatment cohorts. Type III analysis will be used to get the cohort effects conditional on all covariates listed above in Section 4.1.

For event rates, the numerator will be the number of AEs of interest, including repeat occurrences in individual subjects. The denominator will be the total exposure in 100 patient-years, without censoring the exposure to the first event. That is, the total summation of individual patient-years divided by 100. No confidence intervals will be computed for event rates.

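### Does the hazard-ratio rule in SAP 3.6 (baseline Cimzia against everyone else) contradict the exposure-based contrasts in SAP 8.1.3?

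*SAP*

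**What the plan says.** SAP 3.6 sets up several groupings in turn.

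- **Enrolment cohort**, Cimzia or Comparator: "These are the default treatment groups".
- **Actual treatment at baseline**, in three groups: *Cimzia at BL*, *No Cimzia at BL* and *Gap*. The first of these has a lookback rule, which reads "If a patient received Cimzia up to 70 days prior to baseline (half-life of CZP), the patient is a member of the treatment group" and then gives that first label. The next sentence is the one in question: "For the calculation of the Hazard Ratio, the group 'Cimzia at BL' is compared against the combined group" of *No Cimzia at BL* and *Gap*. The paragraph holding both opens with a statement about adverse event tables.
- **Malignancy groups** (two) and **acute-event groups** (five: Cimzia, Comparator, Overlap, Gap, Any Cimzia), directly afterwards.

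Earlier, 3.6 says "Three comparisons may be used to reflect these treatment changes over time and provide context for events reported to the registry" and refers to 8.1.4 for details.

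Hazard ratios are reported in two places. SAP 5.1 does so for time to discontinuation, by enrolment cohort and by actual treatment at baseline. SAP 8.1.3 does so for each adverse event of interest. It opens with "Please refer to Section 3.6 for the assignment of treatment groups" and then sets three contrasts: Cimzia against Comparator and Any Cimzia against Comparator under the acute rules, and Cimzia against Comparator under the malignancy rules. Of the first it says "The comparison of interest is Cimzia vs. Comparator".

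**The concern.** The rule in 3.6 names no analysis, sits in a paragraph that begins with adverse event tables, and is in the section to which 8.1.3 sends the reader for its groups. Applied to adverse events of interest, it would conflict with all three contrasts in 8.1.3. The groups would be fixed at baseline and gap time pooled into the reference. Under the acute rules, gap is a separate state and exposure ends at "Last dose date + treatment class-specific half-life exposure for product" or earlier. Under the malignancy rules, a patient counts as Cimzia permanently from first exposure. SAP Amendment 5 was written to make these analyses follow actual exposure. Malignancy is the primary outcome, so two possible hazard ratios for it would matter.

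The forward reference also looks wrong: 8.1.4 describes rate calculations and one Poisson model and lists no three comparisons.

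If the sentence belongs to 5.1 instead, a smaller question arises. Cimzia Cohort patients may receive their first dose up to 2 months after enrolment, plus a 7-day window (SAP 3.4). Those not already on Cimzia would fall in the non-Cimzia reference. Censoring rule A in 5.1 is worded by cohort and, read that way, does not censor them when they start Cimzia.

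**Working it through.** **1. Which hazard ratio does 3.6 govern?**

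| Feature | 3.6 sentence | 5.1 discontinuation | 8.1.3 adverse events of interest |
|---|---|---|---|
| Grouping | actual treatment at baseline | enrolment cohort, and actual treatment at baseline | exposure over time |
| Baseline labels fit | yes | yes | no, never used |
| Gap | pooled into reference | not specified | separate state (acute); assigned to prior treatment (malignancy, 3.2.1.1) |
| Groups in 3.6 that match | baseline list just before the sentence | same list | malignancy and acute lists just after the sentence |

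The pointer from 8.1.3 to 3.6 therefore lands on the right groups, a few lines below the sentence. Only 5.1 pairs a hazard ratio with the baseline grouping. The specific text of 8.1.3 governs adverse events of interest.

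**2. What would misreading cost?** The plan states no figure to reproduce, so this is an illustration. Assume a true Cimzia-to-Comparator rate ratio of 1.5, a gap rate g times Comparator, and a reference group with 5% / 70% / 25% of its time on Cimzia / Comparator / Gap. The person-time-weighted ratio is

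(c × 1.5 + k + u × g) / (0.05 × 1.5 + 0.70 + 0.25 × g),

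where c, k and u are the baseline-Cimzia group's shares of time on Cimzia, Comparator and Gap.

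- g = 0.5, shares 0.3 / 0.4 / 0.3: 1.00 / 0.90 = 1.11.
- g = 0.5, shares 0.8 / 0.1 / 0.1: 1.35 / 0.90 = 1.50.
- g = 1.0, shares 0.5 / 0.3 / 0.2: 1.25 / 1.025 = 1.22.

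The two rules estimate different quantities. This matters only if an analyst sets 8.1.3 aside.

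**3. Size of the 5.1 question.** From the documents: 1371 Cimzia and 1674 comparator patients, 8% annual drop-out, 8 years. Assumed: a share p of the Cimzia Cohort first dosed after baseline.

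- Mean follow-up = (1 − 0.92^8) / (−ln 0.92) = 5.84 years. Comparator person-time = 1674 × 5.84 ≈ 9773 patient-years.
- Longest time to first dose = 2/12 + 7/365.25 = 0.186 years.
- Starters s = 1371p. Share of reference patients = s / (1674 + s). Share of reference person-time if censored at first dose = 0.186s / (9773 + 0.186s).

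The hazard ratios below are large-sample Cox limits with exponential hazards over 8 years. Comparator and established Cimzia are both at 0.08 per year (true ratio 1.00); starters are at 0.12 (1.5 times) or 0.0533 (0.67 times).

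| | p = 0.3 | p = 0.5 | p = 0.7 |
|---|---|---|---|
| Starters | 411 | 686 | 960 |
| Share of reference patients | 19.7% | 29.1% | 36.4% |
| Share of person-time if censored at first dose | 0.8% | 1.3% | 1.8% |
| HR, 1.5 times, followed throughout | 0.919 | 0.884 | 0.858 |
| HR, 1.5 times, censored at first dose | 0.997 | 0.995 | 0.994 |
| HR, 0.67 times, followed throughout | 1.076 | 1.116 | 1.148 |
| HR, 0.67 times, censored at first dose | 1.002 | 1.003 | 1.004 |
| Loss of reference person-time from censoring | 19% | 28% | 35% |

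With equal hazards the ratio is 1.000 either way. The rows for starters followed throughout are nearer to outer limits than to expectations. Rule B already censors a starter who comes from another biologic, and rule A censors Cimzia Cohort patients who later move to Comparator. Gap patients and later switchers are not modelled. Person-years are also on the high side, because the study closed on 28 August 2020: with uniform enrolment from January 2009 to March 2017 (assumed), mean follow-up is about 5.1 years.

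**The case for a change.** The strongest case for a change is that the reconciliation is inference. Sections 3.6 and 5.1 do not refer to each other on this point, the paragraph does begin with adverse event tables, and a few added words would remove all doubt. That is true as a comment on drafting: 3.6 should have named its analysis, and 8.1.4 does not list the comparisons for which it is cited. But the added words would only confirm what the context already gives, and no reported number would differ.

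Redirecting the reference on the three comparisons to 8.1.3 is less safe than it looks. The 3.6 sentence closely follows Protocol 6.2, which announces two comparisons, one of event rates and one of the case-crossover type. A pointer to the rate section fits that origin. Three contrasts in 8.1.3 match the count, which does not show that they are the ones meant.

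On 5.1, it is fair that rule A does not say how it applies to the baseline groups, and that SAP 8.2 removes patients after a switch while 5.1 does not repeat this. However, cohort need not mean enrolment cohort: 8.1.4 speaks of "differences in incidence rates between actual treatment cohorts". Read by baseline group, rule A would censor non-Cimzia patients when they switch to Cimzia. Censoring at first dose is also not clearly better. It takes starters almost wholly out of a comparison whose stated purpose is to show how actual baseline treatment differs from enrolment cohort, it shortens reference follow-up, and it may itself be informative.

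**Conclusion.** No change follows. The unnamed hazard ratio and the loose reference to 8.1.4 are drafting slips that an analyst resolves from the surrounding text: 5.1 takes the baseline grouping, and 8.1.3 takes its own contrasts for adverse events of interest. On that reading no adverse-event hazard ratio, including the one for malignancy, is affected.

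What remains is a trade-off in the by-baseline discontinuation analysis. Its size is unknown. The range of 0.86 to 1.15 around a true 1.00 rests on assumed shares of 30% to 70% and assumed hazards of 0.67 to 1.5 times comparator, and its direction reverses with the hazard assumption. The result is descriptive, with no formal testing, and the enrolment-cohort hazard ratio, which uses the default grouping, is unaffected. The conclusion depends on the specific text of 8.1.3 prevailing over the general sentence in 3.6, which is the ordinary way to read an analysis plan and agrees with the purpose of Amendment 5.
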